8.1.4 Summaries of Baseline Characteristics, Demographics, and Other Analyses

Demographic variables (i.e. age, gender), socioeconomic variables, prior and concomitant therapies, and BMD absolute values (including FRAX® score) will be summarized overall and by age and/or region, and presented either by descriptive statistics (i.e. mean+- standard deviation for normal distribution or median for skewed variables) or categorical tables (number and proportion).

For all study variables, **no imputation** will be made for any missing values. In terms of FRAX calculation, missing values will be imputed as 'normal'.

8.2 Bias

8.2.1 Methods to Minimize Bias

A two-stage randomized cluster sampling for the study with all demographic resources may minimize volunteer effect, for example, participants with older age and pre-existing fractures; nonresponse bias may be lessened by endeavours by the investigator for advance notification and follow-up with the study invitation. Recall bias may occur in all subjects especially women without a fracture or osteoporosis history (easily forget part of

clinically relevant medications, i.e. commercial calcium supplements or vitamin D preparations). Self-reporting fracture history may be validated by document and/or physical examination, if it is involved in the diagnosis of osteoporosis. The investigator may encourage the subject recall health status and collect all possible evidence documents to verify the subject's claims in the questionnaire. These documents may be from, but not limited to, the subject's medical records, hospital records/database, and/or private insurance documents. Measurement biases will be minimized by DXA machine calibration, quality control by the site and study team, and blinded fracture adjudication by experienced radiologists. For reliability and validity, a pilot testing of the questionnaire will be performed. Moreover, statistical methodology will be appropriately selected to avoid analysis biases in terms of variability in variables including BMI and BMD.

8.2.2 Adjustment for Multiple Comparisons

This is no adjustment for multiple comparisons for study analyses.

8.2.3 Limitations

Despite methods to minimize potential biases or imprecision in the study, there are several limitations of the study. Due to a cross-sectional design, a snapshot in time of the disease is given and thus the incident of vertebral fractures over time cannot be assessed. Although random sampling method is adopted in the study, concerns in a low response to study invitation, subject dropout and random errors may still exist, which may confound the study results and interpretations.

8.3 Sample Size and Power Calculations

The sample size of the study was calculated based on prevalence data per age group several large epidemiological studies [29-32, 36]. As the prevalence of vertebral fractures increases with age, the sample size will be determined as per age group by setting a lower limit for each assumed age-based prevalence rate (Table 8.3.1), using Clopper-Pearson exact method [52] to compute the lower bound of the corresponding 95% CI at a 5% precision. A sample size of 545 at each geographic region will be statistically sufficient to cover all age groups in detecting the prevalence of vertebral fractures, assuming a 5% withdrawal rate for the spinal radiographs in the study. Considering geographic distribution (5 regions), a total sample size of approximately 2700 postmenopausal women aged 50 or above will be enrolled for the study. In addition, this sample size will yield a generally over 90% power at a 0.05 significance level to detect a geographic impact for the fracture prevalence by an odd ratio at 1.40 or 1.50, by using a univariate logistic model in estimating the change in probability.

Assuming a 40% nonresponse rate in population-based studies [56] and 5% ineligibility rate [32], invitation letters will be posted to approximately 4750 women in all regions.

Table 8.3.1 Sample Size Calculation by Age Group based Prevalence

Age group	Sample size	Assumed Prevalence	95% CI Lower Limit
50 - 54	44	5.0%	1.0%
55 - 59	81	7.0%	3.0%
60 - 64	100	12.0%	6.0%
65 - 69	90	16.0%	10.0%
70 - 74	80	20.0%	12.0%
75 - 79	70	23.0%	15.0%
>80	53	37.0%	26.0%

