8.1 Statistical Methods

This section outlines the statistical analysis strategy and procedures for the study. If, after the study has begun, changes are made to primary and/or key secondary hypotheses, or the statistical methods related to those hypotheses, then the protocol will be amended. Changes to exploratory or other non-confirmatory analyses made after the protocol has been finalized, along with an explanation as to when and why they occurred, will be listed in the CSR for the study. Post hoc exploratory analyses will be clearly identified in the CSR. A separate SAP will be created for this study.

8.1.1 Primary Objective(s): Calculation of Epidemiological Measure(s) of Interest (e.g. descriptive statistics, hazard ratios, incidence rates, test/retest reliability)

The study's primary objective is to investigate the prevalence of radiographic vertebral fractures in community-dwelling postmenopausal women in China. Descriptive statistics will be made to statistically address this objective. No hypothesis testing will be applied in the study for this primary objective.

Point estimates (percentage) of prevalence by overall study population and by age group and/or geographic region will be calculated and displayed. A fracture case is defined and counted as the subject with the presence of at least one vertebra classified as grade 1, 2, or 3 semi-quantitatively by Genant's score as agreed by both study radiologists.

Point estimates of prevalence rates by overall and geographic region will be adjusted by a nationwide age distribution using the database from Basic Statistics on National Population Census 2010, National Bureau of Statistics of China [53]. A direct method of adjusting rates will be made to give age-standardized prevalence. Age-standardized rate by regional age distribution data may be calculated subject to site location and will be specified in the SAP before database lock and study analyses.

A corresponding two-sided 95% confidence interval (CI) for each individual point estimate will be given. This 95% CI is based on a direct calculation of the exact binomial distribution. A more conservative method, the Wilson Score CI [52], will be applied to give 95% CIs for all point estimates and compared with the exact binomial distribution.

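### Section 8.3 gives the age-group sizing a 5% precision that its own table does not show, and most of the tabulated limits are one-sided bounds although two-sided intervals are planned

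*Combined protocol and SAP*

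**What the plan says.** Section 8.3 sets a separate lower limit for each age group's assumed prevalence. It then uses the Clopper-Pearson exact method "to compute the lower bound of the corresponding 95% CI at a 5% precision". Table 8.3.1 lists, for seven age groups, the sample size, the assumed prevalence and a lower limit headed as belonging to a 95% CI. The text concludes: "A sample size of 545 at each geographic region will be statistically sufficient to cover all age groups". That figure allows for a 5% loss of spinal radiographs, and five regions give about 2700 women.

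For the analysis, Section 8.1.1 says: "A corresponding two-sided 95% confidence interval (CI) for each individual point estimate will be given". The intervals are exact binomial, with Wilson score intervals alongside. Table 8.1.1.1 includes rates by age group within region, each with a 95% CI.

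**The concern.** The primary objective is descriptive and has no hypothesis test, so interval width is what justifies the sample size for it. The odds-ratio power statement in Section 8.3 is an addition to that. A reader who meets a 5% precision will naturally take it to mean estimates good to about 5 percentage points. The columns of the same table show otherwise for most groups. The table also omits the upper side, which is wider.

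The age-by-region cells will be reported, and they are the cells the table sizes. Someone relying on the phrase could over-read regional differences within an age group. There is also a mismatch to settle: if the printed limits are one-sided bounds, they are not the limits that the planned two-sided intervals will produce.

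**Working it through.** **Inputs.** Sample size n, assumed prevalence p and printed lower limit come from Table 8.3.1. The method (Clopper-Pearson) comes from Section 8.3, and the two-sided 95% interval from Section 8.1.1.

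**Step 1: reproduce the total.** 44 + 81 + 100 + 90 + 80 + 70 + 53 = 518, and 518 / 0.95 = 545.3. This agrees with the stated 545 per region, so each table row is one age-by-region cell.

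**Step 2: read precision off the table.** Prevalence minus printed limit is 4, 4, 6, 6, 8, 8 and 11 points. Five of seven exceed 5. As a share of prevalence the distances run from 11/37 = 30% to 4/5 = 80%, so a relative reading does not fit either.

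**Step 3: reproduce the printed limits.** With x = n·p (not rounded), the lower bound is the t-quantile of Beta(x, n − x + 1) and the upper bound is the (1 − t)-quantile of Beta(x + 1, n − x). Use t = 0.05 for a one-sided 95% bound and t = 0.025 for a two-sided 95% interval.

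| Age | n | p | Printed limit | One-sided lower | Two-sided lower to upper | Distance below / above (points) |
|---|---|---|---|---|---|---|
| 50-54 | 44 | 5% | 1% | 1.0% | 0.7 to 16.1% | 4.3 / 11.1 |
| 55-59 | 81 | 7% | 3% | 3.0% | 2.5 to 14.9% | 4.5 / 7.9 |
| 60-64 | 100 | 12% | 6% | 7.1% | 6.4 to 20.0% | 5.6 / 8.0 |
| 65-69 | 90 | 16% | 10% | 10.0% | 9.1 to 25.2% | 6.9 / 9.2 |
| 70-74 | 80 | 20% | 12% | 13.0% | 11.9 to 30.4% | 8.1 / 10.4 |
| 75-79 | 70 | 23% | 15% | 15.0% | 13.8 to 34.6% | 9.2 / 11.6 |
| 80+ | 53 | 37% | 26% | 25.9% | 24.1 to 51.4% | 12.9 / 14.4 |

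The one-sided column matches five rows. Solving for the smallest n that reaches each printed limit gives, in table order:
- one-sided: 44, 81, 64, 90, 61, 70, 54. Four rows are exact and 80+ differs by one.
- two-sided: 58, 110, 87, 123, 83, 96, 74. No row agrees with the plan.

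The 60-64 and 70-74 rows fit the one-sided pattern only if their limits were 7% (n = 97 against 100) and 13% (n = 81 against 80).

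**Step 4: compare the printed limits with the planned intervals.** The two-sided lower limit is below the printed one in six rows. The shortfall is 0.3 to 1.9 points in five of them and 0.1 point in 70-74. Only 60-64 clears its printed limit (6.4% against 6%). On the upper side no cell is within 5 points.

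**Step 5: precision at the wider reporting levels** (two-sided exact).
- Age group over five regions (5n): 2.3 to 4.8 points for ages under 80, and 5.8 below / 6.1 above for 80+.
- One region, crude: the cells' expected cases sum to 85.98, so p = 85.98 / 518 = 16.6%. With n = 518 the distances are 3.1 below / 3.5 above.
- Overall, crude: with n = 5 × 518 = 2590 they are 1.4 below / 1.5 above.

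These are simple-binomial figures. The documents give no design effect for the cluster sampling of Sections 3.1 and 3.2. As an assumption, design effects of 1.5 and 2 multiply the distances by about √1.5 = 1.22 and √2 = 1.41. The overall 1.5 then becomes about 1.8 to 2.1, and the regional 3.5 about 4.3 to 4.9.

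**The case against.** A reader might infer that the plan set a 5-point target and that five of seven cells miss it. The documents do not support that. Section 8.3 never defines the 5% as a distance from prevalence to limit. Its sizing rule is a different lower limit for each group, and those limits are printed openly. The 5% stands in the clause about computing the exact bound, and a 5% lower tail is what reproduces five of the seven limits. On that reading no cell fails a stated target. This stands, and it is why the point is about a wrong label and not about an unmet goal.

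It can also be said that little harm follows: the lower limits are in the same table, the report will show the actual interval for every cell, and Section 8.1.1 already makes the primary analysis descriptive. That also stands, and it limits the point to a correction of the document.

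What does not stand is the idea that the tail-level reading makes the text correct. If 5% is a tail level, no precision is stated at all. The column headed as a 95% CI limit then mostly holds one-sided bounds, which differ from the intervals planned in Section 8.1.1, and two rows still do not follow the pattern.

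**Conclusion.** The point holds as a misstatement of the design's precision and of the sidedness of the tabulated limits. The subtraction in step 2 needs no assumption. That the 5% is a one-sided tail is an inference from the five matching rows; the documents do not say it. The recomputed limits assume an observed proportion equal to the assumed prevalence, fractional counts, and independent observations.

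In size, an age-by-region cell has two-sided distances of 4.3 to 12.9 points below and 7.9 to 14.4 above. The 80+ interval is about 27 points wide. Pooled over regions, every age group except 80+ is within 5 points on both sides before any design effect. So the phrase misdescribes the cells that the table sizes, more than the pooled estimates. Nothing here shows that enrolment is too small, because the documents set no numerical width that the cells must meet.

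**What to change.** In Section 8.3:

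1. Delete the 5% precision phrase. If a one-sided 5% tail was meant, say so in those terms.
2. Replace the lower-limit column of Table 8.3.1 with the two-sided 95% exact lower and upper limits at the planned sizes, as in the working table. Alternatively, keep a lower-limit column, label it one-sided 95%, and correct the 60-64 and 70-74 rows to 7.1% and 13.0%.
3. State the expected precision by reporting level: age-by-region cell about 4 to 13 points below and 8 to 14 above; age group over all regions about 2 to 6; crude rate per region about 3.1 to 3.5; crude overall rate about 1.4 to 1.5. Mark these as simple-binomial figures before any design effect or age standardisation. Without that mark the regional and overall figures could themselves be too favourable.

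The cost is a wording and table change in the protocol, carried into the separate SAP. Enrolment, estimates and planned intervals do not change. The downside is that the stated figures look less favourable.

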3.5 Stratification

The subjects will be sampled and stratified according to the following factors:

- 1) Age;

Seven (7) age groups: 50 - 54, 55 - 59, 60 - 64, 65 - 69, 70 - 74, 75 - 79, 80 or above;

- 2) Geographic region;

Five (5) regions in China: North, South, Southeast, Southwest, and Central

4 Variables and Epidemiological Measurements

All eligible participants will be included in the study to an endocrinologist, or other specialist, whenever appropriate, for the collection of all clinical and radiological information by 1 onsite study visit in a cross-sectional fashion. Spine radiograph and/or DXA may be separated from onsite interview by a follow-up visit as determined by the investigator.

Questionnaire

All demographic data, socioeconomic status, lifestyle information, and clinical features including medical history/concomitant medications, will be collected by an interviewer-administered questionnaire performed by the investigator. The questionnaire will be designed to adapt China's cultural and clinical practice. The analyzable variables derived from the questionnaire include (but not limited to):

- Age (absolute value and category);
- Place of birth and dwelling geographic region;
- BMI (height and weight, as measured in the site);
- Social status and lifestyle (educational level, occupation, monthly income, physical exercise, diet, smoking, alcohol intake, diet, calcium intake);
- Clinical features (age and years of menopause, medical history, history of osteoporosis and parental osteoporosis, any prior fractures, prior and concomitant medication, antiresorptive treatment, glucocorticoid treatment, other treatment reducing bone mass);
- FRAX score (as determined by self-reported fracture and radiology evidence and calculated based on the information from questionnaire with/without BMD).

BMD Measurement

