To test reproducibility for fracture adjudication, intra- and inter-observer reliabilities will be tested using a sample of first 100 X-ray films from any participating site in the study. Intra-observer and inter-observer agreement will be calculated by kappa statistic. A κ is 0.81 or above suggests very good agreement.

The statistical analyses for primary objective are summarized in Table 8.1.1.1.

Table 8.1.1.1 Statistical Analysis Approaches on Primary Objective

VF Prevalence	Rate	Estimate*
Overall	Crude/Age-Standardized Rate	Point and 95% CI
Age Group§	Crude Rate	Point and 95% CI
Region^	Crude/Age-Standardized Rate	Point and 95% CI
Age Group and Region△	Crude Rate	Point and 95% CI
Genant's Grade※	Crude Rate	Point and 95% CI

* Based on exact binomial distribution 95% CI and Wilson Score 95% CI;
§ Age group will be given by 50 – 54, 55 – 59, 60 – 65, 65 – 69, 70 – 74, 75 – 79, and 80+; and by < 65 and ≥ 65;
^ Participating sites will be grouped by 5 regions in China: North, South, Southeast, Southwest, and Central;
△ Prevalence rate will be presented by all age groups and overall in individual regions in China;
※ Genant's Grade by 1, 2 or 3.

8.1.2 Secondary Objective(s): Calculation of Epidemiological Measure(s) of Interest (e.g. hazard ratios, incidence rates, test/retest reliability)

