8.1.2.2 Risk Factors for Radiographic Vertebral Fracture or Densitometric Osteoporosis

As secondary objectives, all possible factors including socioeconomic status, lifestyle and clinical parameters will be assessed to identify if they are the risk factors of a prevalent vertebral fracture or densitometric osteoporosis in Chinese postmenopausal women.

A two-step statistical modeling will be established to assess the potential risks against the response of analysis interest (dependent variable). Initially, a single logistic regression for bivariate analysis will be used to give a percentage tabulation presenting proportions of case (morphometric vertebral fracture or densitometric osteoporosis) versus control by each analysis parameter. An odds ratio and associated probability (P value) will be given to examine the statistical significance of this independent variable in the model. A P value of 0.25 or less will be the criterion [54] for an entry into a multivariate logistic model for all estimated variables. Also, all clinically relevant variables, regardless of a probability level, will be included in the final model at the discretion of the study team.

Finally, a multivariable logistic regression model will be constructed for both dependent variables. A stepwise backward method to eliminate non-significant variables will be performed until all remaining variables in the model have a P value less than 0.1. The goodness-of-the-fit will be evaluated by using deviance and likelihood ratio tests and Hosmer–Lemeshow test [55] to assess if there is any single important variable missing from the model.

In the bivariate and multivariate analysis, age, BMD, and BMI will be fitted as continuous variables. Geographic region grouping study sites will be fitted as a categorical variable. Due to potential collinearity of BMD to vertebral fracture, BMD will also be introduced as a dichotomous variable (osteoporosis vs. normal and osteopenia). BMI may vary among study sites in the study, odds ratio per unit BMI instead of per standard deviation to minimize the biases upward.

8.1.3 Exploratory Objective(s): Calculation of Epidemiological Measure(s) of Interest (e.g. hazard ratios, incidence rates, test/retest reliability)

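### Section 8.3 claims over 90% power for a geographic effect at an odds ratio of 1.40 or 1.50 without naming the contrast, and at 1.40 the figure does not describe the five-level region factor the plan fits

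*Combined protocol and SAP*

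**What the plan says.** Section 8.3 first derives the sample size from age-specific prevalences (Table 8.3.1), which leads to 545 women per region and about 2700 in total, "assuming a 5% withdrawal rate for the spinal radiographs in the study". It then adds a power statement: "this sample size will yield a generally over 90% power at a 0.05 significance level to detect a geographic impact for the fracture prevalence", for an odds ratio of 1.40 or 1.50, "by using a univariate logistic model in estimating the change in probability". It does not say which regions are compared, what prevalence the odds ratio is applied to, whether the test is one- or two-sided, or how many evaluable women are assumed.

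Elsewhere the plan is specific about region. Section 3.5 lists "Five (5) regions in China: North, South, Southeast, Southwest, and Central", and the footnote to Table 8.1.1.1 groups the sites in the same way: "Participating sites will be grouped by 5 regions in China: North, South, Southeast, Southwest, and Central". Section 8.1.2.2 says "Geographic region grouping study sites will be fitted as a categorical variable", which makes region a factor with 4 degrees of freedom. Backward elimination in that model runs "until all remaining variables in the model have a P value less than 0.1". Section 8.2.2 states: "This is no adjustment for multiple comparisons for study analyses". No section combines the five regions into two groups.

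**The concern.** A reader of section 8.3 would take it that a regional odds ratio of 1.40 will be missed less than one time in ten. The natural reading of a geographic effect in this plan is the region factor that is fitted, or a comparison between regions within it. If power for those is well below 90%, the statement promises more than the analysis delivers. A region term that drops out of the risk-factor model could then be read as evidence that the regions do not differ. This touches one covariate in the secondary risk-factor analysis, and it does not touch the primary objective, which has no hypothesis test.

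**Working it through.** **Inputs.**
- Baseline prevalence: section 8.3 gives none for this calculation. The rows of Table 8.3.1 sum to 518 women, and prevalence times size sums to 85.98, so the weighted prevalence is 85.98/518 = 16.6%. Section 1.1 gives 15% for Chinese women aged 50 or over. I use 15% to 16.6% as the lowest-region prevalence p0. This is an assumption.
- N: 2700 enrolled (540 per region), or 0.95 x 2700 = 2565 evaluable (513 per region).
- Two-sided 0.05 (sidedness is not stated), equal regions, no design effect, no multiplicity adjustment.
- Odds ratio (OR) 1.40 or 1.50, read as the largest OR between any two regions.

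**Formulas.**
- p1 = OR x p0 / (1 - p0 + OR x p0). For p0 = 0.166 and OR 1.40: 0.2324/1.0664 = 0.218. For OR 1.50: 0.230. For p0 = 0.15: 0.198 and 0.209.
- Two groups: power = Φ[(|p1 - p0| - 1.96 s0)/s1], with s0 the pooled standard error under the null and s1 the unpooled one.
- Five-level factor: noncentral chi-square on 4 df, critical value 9.49, Pearson noncentrality λ = n Σ(pi - p̄)² / [p̄(1 - p̄)] with n women per region, checked against the likelihood-ratio noncentrality.

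**Reproducing the stated figure.** Split 2700 women 50/50, with p0 = 0.166 and OR 1.40. The difference is 0.0519, s0 = 0.0152 and s1 = 0.0151, so (0.0519 - 1.96 x 0.0152)/0.0151 ≈ 1.47 and power is 92.9%. At OR 1.50 it is 98.7%. Two regions pooled against three give 92.0% and 98.3%. So a figure over 90% is obtainable for two large blocks of the whole sample.

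**The planned factor, p0 = 0.166, OR 1.40, 513 per region.**
- Two single regions: s0 = 0.0246, s1 = 0.0245; (0.0519 - 0.0482)/0.0245 ≈ 0.15; power 56%.
- One higher region against four: s0 = 0.0188, s1 = 0.0200; (0.0519 - 0.0368)/0.0200 ≈ 0.75; power 77%.
- 4-df test, two regions high and three low: p̄ = 0.187, λ ≈ 10.9 (likelihood ratio 10.8); power 75-76%. With 1.40 as the largest OR, this two-against-three pattern is the most favourable; 20,000 random patterns in each of three input sets gave nothing higher.

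**Ranges over p0 15-16.6% and N 2565-2700.**

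| Contrast | OR 1.40 | OR 1.50 |
|---|---|---|
| Two single regions | 53-58% | 70-75% |
| One higher region v the other four | 74-79% | 89-92% |
| 4 df, two high and three low (best case) | 72-78% | 89-93% |
| 4 df, one region higher | 53-61% | 72-80% |
| 4 df, evenly graded | 41-46% | 58-65% |
| Pooled two v three regions | 88-92% | 97-98% |
| Pooled 50/50 split | 90-93% | 97-99% |

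Likelihood-ratio simulation (100,000 runs, 513 per region, p0 = 0.166) agrees. For OR 1.40 and 1.50 it gives 56.4% and 73.5% pairwise, 76.3% and 90.3% for one region against four, and 75.2% and 91.1% for the best 4-df pattern.

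**Sensitivity at OR 1.40.**
- Baseline 18-20%: the best cases (one region v four, best 4-df pattern) rise to about 78-84%.
- Baseline needed for 90%: 27-31% for one region v four, 26-29% for the best 4-df pattern. A pair of regions never reaches it (maximum 77-79%).
- One region 1.40 above and another 1.40 below three middle regions, so that the extremes differ by 1.40² = 1.96: the 4-df test has 89-93%.

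**The case against.** Section 8.3 does not say that its figure is for the 4-df factor or for a pair of regions, and the figure can be reproduced for a two-block comparison. A reader might infer that the sponsor made an arithmetic error. The documents do not support that: what they show is an unnamed contrast and a mismatch with the planned factor.

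The ceiling also depends on inputs that section 8.3 leaves open. A reader might take about 79% as a fixed upper limit. It is not: it moves with the baseline, and a one-sided 0.05 test of one higher region against four gives 83-87%. If 1.40 is measured from a middle reference in both directions, the 4-df test reaches about 90%. All of this stands. Within the range considered, however, neither a higher baseline (up to 20%) nor a one-sided test brings the planned comparisons to 90%, and the wider-spread reading is not what section 8.3 states.

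The harm is limited as well. Table 8.1.1.1 reports crude and age-standardised prevalence with 95% confidence intervals for each region, whatever the model retains. Section 8.1.2.2 lets the study team keep clinically relevant variables regardless of P value. Its entry screen is P of 0.25 or less, where power at OR 1.40 is 92-95% for the best 4-df pattern and 92-94% for one region against four, though 81-85% pairwise and 74-78% graded. At the P < 0.1 retention level it is at most 83-87% for one region against four, at most 81-86% for the 4-df test, and 65-70% pairwise. These last figures are approximate, because they apply univariate power to a multivariable step.

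**Conclusion.** The point holds as a mismatch between a stated power and the planned analysis. Under the assumptions listed, an OR of 1.40 as the largest regional difference would be missed at least about two times in ten at the 0.05 level, and more than four times in ten between two single regions, against the less than one in ten implied. At a baseline of 18-20% the best cases are still missed roughly 16-22 times in 100. At OR 1.50 the statement is roughly right for one region against four and for the best 4-df pattern, and wrong for pairs and graded differences. A design effect for women clustered within the 8-10 sites would lower every figure.

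A reader might go further and conclude that 2700 is too few or that the regional results are unreliable. Neither follows. The target comes from the age-specific precision calculation, the primary analysis is descriptive, and the regional prevalences with their intervals do not depend on this sentence.

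**What to change.** Replace the power sentence in section 8.3 with one that names the contrast and its direction, the baseline, the sidedness and the evaluable N, and gives each odds ratio separately. For example:

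> With 2700 enrolled (about 513 evaluable women per region), a prevalence of 16.6% in the lower regions and a two-sided 0.05 test, before any design effect for sites, one higher region against the other four has about 77% power at an odds ratio of 1.40 and 91% at 1.50. Two single regions have about 56% and 73%. The 4-df test has at most about 75% and 91% when these are the largest odds ratios between regions.

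If a pooled split or a wider regional spread was intended, say so and add that contrast to section 8.1.2.2 or to the separate SAP. The change is one sentence, with no extra participants and no change to the primary analysis. Its downside is a less favourable power statement at 1.40.

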3.2 Study Population

This study will include approximately 2700 community-dwelling postmenopausal women aged 50 or above at 8 - 10 participating sites throughout China. A two-stage cluster sampling will be performed for the study. Firstly, geographic regions are divided into 'clusters' and then a randomized stratified sampling will be performed by age group using a computerized random selection on various demographic records (as indicated in Section 3.1) from the participating sites and the communities by which they cover. All subjects are expected to have an interview for questionnaire, vertebral imaging and BMD measurement. To be eligible for the study, participants must fulfill the following inclusion and exclusion criteria (Section 3.3 and 3.4):

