6.1.1 Administrative Procedures

6.1.1.1 Randomization and Study Invitation

In the study, 5 geographic regions will be identified as 'clusters' at the first stage. Within a region, a computer-generated randomization list by stratum (age) will then be produced separately in each participating site to identify and select specific invitees. All possible resources securing the participant's bio-information and contact details will be utilized to generate a full list of potential invitees. These resources include, but not limited to, Government resident lists, community-dwelling records, city council records, primary care health records and/or local health insurance records. Based on the sequence of the list, a numbered letter will be sent out to all women who are 50 years of age (inclusive) or above from the investigator to enquiry of their wish to attend the study. The letter to the women selected will explain the nature, the objectives and the study elements of the study. The receipt and acceptance of invitation will direct to the investigators by telephone, email, return of letter, or showcase the letter at the time of onsite screening. An advance notification by telephone or email may be practiced by the site investigator and/or study authorized staff to increase the rate of invitation acceptance.

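### The over-90% power and 0.05 level stated for a geographic effect hold only if sites within a region have the same true fracture prevalence

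*Combined protocol and SAP*

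**What the plan says.** Section 8.3 sizes the study on age-specific prevalence, with "A sample size of 545 at each geographic region". A further sentence says that about 2700 women give "over 90% power at a 0.05 significance level to detect a geographic impact for the fracture prevalence". The effect sizes named there are odds ratios of 1.40 and 1.50, and the model is a logistic regression with one covariate. The section does not name the contrast between regions or the baseline prevalence.

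On structure:
- Section 3.2 plans "approximately 2700 community-dwelling postmenopausal women aged 50 or above at 8 - 10 participating sites throughout China".
- The footnote to Table 8.1.1.1 states: "Participating sites will be grouped by 5 regions in China: North, South, Southeast, Southwest, and Central".
- Section 6.1.1.1 has the age-stratified random list "produced separately in each participating site to identify and select specific invitees".

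On analysis, Section 8.1.2.2 states: "Geographic region grouping study sites will be fitted as a categorical variable". Candidate variables enter the multivariable model at P of 0.25 or less and are eliminated backward until all remaining P values are below 0.1. The supplied text contains no site term, random effect, cluster-robust variance, ICC or design effect, and the limitations in Section 8.2.3 do not mention clustering.

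**The concern.** Every woman at a site has the same region, so the replicates for a regional comparison are the sites. Eight to ten sites over five regions average 8/5 = 1.6 to 10/5 = 2.0 per region; the allocation is not stated. A woman-level logistic model judges regional differences against binomial noise among some 2565 women (2700 x 0.95), not against the variation between sites of the same region.

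Section 3.1 aims to represent a geographically generalized Chinese population, so the inference is meant to reach beyond the sampled sites. In that setting, ordinary differences between local communities can appear as a regional effect. At stake are the power statement in Section 8.3 and the reading of the region term in the risk-factor models.

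**Working it through.** **Inputs.** Two-sided alpha of 0.05 (sidedness is not stated), OR 1.40 or 1.50, 2700 women, five regions, 8-10 sites and 5% radiograph loss (Sections 3.2 and 8.3). Evaluable women per region: 2700 x 0.95 / 5 = 513. Baseline prevalence is either 15% (Section 1.1) or the Table 8.3.1 rates weighted by their sample sizes, 85.98/518 = 16.6%. The ICC is assumed.

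**Step 1: reproduce the stated power, women independent.** With p1 = OR x p0/(1 - p0 + OR x p0), power = Phi{[|p1 - p0| - 1.96 sqrt(pbar(1 - pbar)(1/n0 + 1/n1))] / sqrt(p0(1 - p0)/n0 + p1(1 - p1)/n1)}.

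Example: p0 = 0.15, OR 1.40, 1350 v 1350. Then p1 = 0.21/1.06 = 0.198, and (0.0481 - 1.96 x 0.01460)/0.01456 = 1.34, so power is 91%.

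| Contrast, women independent | OR 1.40 | OR 1.50 |
|---|---|---|
| Half v half | 91-93% | 98-99% |
| 2 v 3 regions | 90-92% | 98% |
| 1 v 4 regions | 77-79% | 90-92% |
| One region v another | 55-59% | 72-76% |
| 4-df test, one region raised | 57-61% | 77-80% |

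Reading the odds ratio as a difference between regions or groups of regions, the claim is reproduced at both values only for a split into two large groups. An odds ratio per step along an ordered region score would give about 100%, but the plan treats region as unordered categories.

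**Step 2: false-positive rate with no regional effect.** The between-site SD is sqrt(ICC x 0.166 x 0.834): 1.2, 2.6 and 3.7 prevalence points at ICC 0.001, 0.005 and 0.01.

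With 10 sites, two per region, each site has m = 513/2 = 256.5 women. The test statistic is inflated by D = 1 + (m - 1) x ICC, which is 1.26, 2.28 and 3.56. Approximate rejection rates are then:
- Two-group contrast: 2[1 - Phi(1.96/sqrt(D))] = 8%, 19%, 30%.
- 4-df region test at 5%: P(chi-square on 4 df > 9.488/D) = 11%, 38%, 61%.
- 4-df region test at 10%: P(chi-square on 4 df > 7.779/D) = 18%, 49%, 70%.

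Simulation (beta-distributed site prevalences, binomial counts, at least 20,000 studies per setting) agrees for 10 sites and extends the result to 9 sites (2,2,2,2,1) and 8 sites (2,2,2,1,1):

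| Rejection rate over 8-10 sites | ICC 0 | ICC 0.001 | ICC 0.005 | ICC 0.01 |
|---|---|---|---|---|
| 4-df test, nominal 5% | 5% | 11-14% | 39-49% | 61-72% |
| 4-df test, P<0.1 retention level | 10% | 18-22% | 49-59% | 70-79% |
| Two-group split (e.g. 2 v 3 regions), nominal 5% | 5% | 8-9% | 19-23% | 30-34% |

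The two-group rates are somewhat higher if single-site regions fall together on one side.

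**Step 3: power when region is tested against between-site variation.** Ten sites of 270 women (no radiograph loss, which favours the test), 16.6% baseline, OR 1.40 / 1.50:

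| Site-level test | ICC 0.005 | ICC 0.01 |
|---|---|---|
| 5 v 5 sites | 51% / 67% | 35% / 48% |
| 4 v 6 sites (2 v 3 regions) | 50% / 66% | 35% / 48% |
| F test on 4 and 5 df, one region raised | 14% / 19% | 11% / 14% |

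**The case against.** The other side has a strong case on consequence and size.

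- **Little depends on the claim.** Section 8.1.1 rules out hypothesis testing for the primary objective, Table 8.1.1.1 reports regional prevalence only as estimates with intervals, and Section 2.2 lists no objective of comparing regions. The sample size comes from age-specific lower limits. The 0.05 level for geography appears in one added sentence of Section 8.3. All of this stands and limits the point.
- **The 4-df test is not named in the plan.** Correct. The reading that reproduces the stated power is a two-group split, where the inflation is smaller, so both sets of rates are shown.
- **Site variation may be small.** Section 1.2 describes prevalence as fairly uniform across world regions, and films are standardised and read centrally by blinded radiologists. Central reading removes reader differences between sites. It does not remove differences in community, list source, response (40% nonresponse is assumed) or film acquisition.
- **Sites are not described as a random sample.** If inference stopped at these sites, the woman-level test would be valid. Section 3.1 intends wider inference.
- **A separate SAP is promised (Section 8.1).** It could settle model detail, but the method and power claim as written here would still need correction.

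A reader might infer that the planned test would usually declare a regional effect where none exists. The documents do not support that: they give no ICC, and at 0.001-0.005 the nominal-5% rates above all stay below one half. A reader might also call the power figure void. It is not: it reproduces under independent women and a two-group split. What it lacks is that condition.

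**Conclusion.** The point holds in limited form. For inference about regions beyond the sampled sites, the 0.05 level and the over-90% power are conditional on zero site-to-site variation within a region, and the plan neither states nor supports that condition. A between-site SD of about 1.2 prevalence points (ICC 0.001) already raises the five-region false-positive rate from 5% to 11-14%, and the two-group rate to 8-9%. At ICC 0.005-0.01, a test against between-site variation has power well below 90% for every contrast examined.

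The size depends on the assumed ICC, the 16.6% prevalence and an inferred one or two sites per region. The consequence is confined to the Section 8.3 power sentence and the region term in the Section 8.1.2.2 models.

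**What to change.** 1. In Section 8.3, withdraw the geographic power statement. Alternatively, state that it assumes no site-to-site variation within a region, and name the contrast and baseline prevalence.
2. In Section 8.1.2.2, keep region in the models as a sampling stratum, exempt from the P-value entry and elimination rules. Do not interpret its woman-level P value as evidence of a regional effect.
3. Report each site's age-standardised prevalence within its region, so that the reader can compare the spread between sites with the spread between regions.
4. Optionally, add a random-site-intercept or site-level test of region as supportive only. State its 3-5 denominator degrees of freedom (8-10 sites minus 5 regions), and that site and region cannot be separated in any single-site region. It is too fragile to be the main analysis.

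The cost is wording in two sections and one table, with no new women, sites or data. The downside is that the study no longer claims adequate power for a regional effect, and the regional comparison becomes descriptive.
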